9.1.2.1 Treatment Period

During Visit 2, the following assessments will be completed before the subject receives their first dose of study drug: MMSE, CDR, ADAS-cog14, FAQ, and NPI-10. (revised per Amendment 01) These assessments will provide baseline measurements for the study. For any given subject, every effort should be made to ensure that the CDR rater remains unchanged throughout the study. (revised per Amendment 04) Inclusion and exclusion criteria will be reviewed again together with concomitant medications and assessment of AEs. A single 12-lead ECG will be conducted. All ECG recordings will be evaluated by a central reader. (revised per Amendment 01) The C-SSRS will also be administered. A baseline routine physical examination with dermatologic review, vital signs measurements, clinical laboratory testing (including viral characterization), urinalysis using urine dipstick, and a urine pregnancy test (females of child-bearing potential only), will be performed. Additional blood samples will be taken for PD/exploratory biomarkers and immunologic assessments. (revised per Amendment 04) Some of the immunologic assessment blood sample will be used to prepare isolated PBMCs which will be stored for testing as required. (revised per Amendment 03) The results of some of the immunologic assessments will be provided to the DSMB for periodic review during the Core Study. (revised per Amendments 01 and 06) Whilst there is no prescribed order in which the assessments at each visit are to be performed, the subject component of the cognitive, functional and quality of life assessments are to be performed in the morning whenever possible, or consistently at the same time of the day and ideally should be completed before the more invasive procedures (eg, physical examination, ECG, blood draw).

Subjects will be randomized at Visit 2 (Day 1) to receive elenbecestat 50 mg per day or placebo administered orally QD in the morning with or without food. Subjects will be encouraged to stay at the site for observation for at least 30 minutes following their first dose of study drug. The duration of this observation period can be extended at the investigator's discretion, eg, if warranted by medical history or concomitant medication. (revised per Amendment 04) Double-blinding to study drug will be in effect throughout the Treatment Period.

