9.2.3 Rationale for Clinical Endpoints

The CDR is a clinical global rating scale requiring the interviewing of both the subject and a study partner who knows and has contact with the subject. The CDR is a clinician directed assessment of both cognition and function, and is intended to capture the state and therefore the disease stage of the individual. The CDR has been proposed as an acceptable approach for following disease progression and confirming treatment effects in AD. The cumulative score or CDR-SB is a well-described, validated, and reliable measure of change through the course of AD and has been proposed as a suitable single outcome measure for AD trials in dementia and pre-dementia populations ([FDA 2013 AD Guidelines](#), [EMA 2016 AD Guidelines](#)).

The ADAS-cog is the most widely used cognitive scale in AD clinical studies ([Rosen, et al., 1984](#)). The 14-item version will be used in the present study since it is considered more sensitive for less impaired populations such as MCI/Prodromal and mild AD subjects ([Fleisher, et al., 2007](#)). Furthermore, a separate endpoint for the ADAS-cog14 immediate recall and delayed recall subtests is included. (revised per Amendment 01)

The MMSE is a cognitive instrument commonly used for screening purposes, for staging of disease severity and is often measured longitudinally in AD clinical studies to follow disease progression and treatment effects ([Folstein, et al., 1975](#)).

The FAQ collects information on 10 items concerned with performing daily tasks necessary for independent living. The FAQ is considered as a better indicator of clinical

meaningfulness than cognitive change as it reflects the subject’s functional state and should correlate well with AD progression.

ADCOMS is a weighted linear combination of 12 items from 3 of the above clinical scales, the ADAS-cog, the MMSE, and the CDR. These 12 items consist of the predictive variables A4, A7, A8, A11, M1, M7, C1, C2, C3, C4, C5, and C6. The names of these items and the corresponding scale names are described in [Table 1](#). The data from 4 studies, including the Alzheimer’s Disease Neuroimaging Initiative (ADNI), ADCS-008, E2020-A001-412, and E2020-E033-415 have been used in a statistically validated model aimed at optimizing sensitivity to disease progression over time in the MCI population, allowing earlier detection of clinical change.

Table 1 Predictive Variables for the ADCOMS

Scale	Item ID	Item Name	PLS weight

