9.3.1 Inclusion Criteria

Subjects must meet all of the following criteria to be included in this study:

Core Study

1. MCI due to AD or Mild AD according to the National Institute of Aging – Alzheimer’s Association (NIA-AA) core clinical criteria and must have all of the following at Screening: (revised per Amendment 04)
 - a. MMSE score equal to or greater than 24
 - b. CDR global score of 0.5
 - c. CDR Memory Box score of 0.5 or greater
2. A history of subjective memory decline with gradual onset and slow progression over the last 1 year before Screening; this MUST be corroborated by a study partner
3. Cognitive impairment of at least 1 SD from age-adjusted norms in total recall or delayed recall on the ISLT.
4. Positive biomarker for brain amyloid pathology as indicated by at least 1 of the following:
 - a. PET assessment of amyloid imaging agent uptake into brain. Note: amyloid PET screens will be performed according to local regulatory guidelines and thus may be restricted for those subjects who are not suitable for LP to obtain CSF for testing of eligibility.
 - b. CSF AD assessment (eg, tau: A β (1-42) ratio) (revised per Amendment 04)

NOTE: Subjects may undergo both the amyloid PET and CSF assessments, but need a positive amyloid result in only 1 of the 2 procedures to confirm eligibility. Subjects who consent to amyloid PET or CSF for eligibility purposes are not required to participate in the amyloid PET or CSF longitudinal substudies. Use of a historical amyloid positive PET (conducted within 12 months before the planned date of randomization) is acceptable for determination of eligibility but will not suffice for the baseline assessment if the subject wishes to consent to the amyloid PET longitudinal substudy. The historical imaging data must be made available to the sponsor. Historical CSF samples, if collected, processed, and stored under appropriate conditions and approved by the sponsor, may be analyzed to determine CSF amyloid positivity. (revised per Amendments 04 and 06).
5. Male or female subjects between 50 and 85 years of age, inclusive at the time of consent
6. If receiving an AChEI or memantine or both for AD, must be on a stable dose for at least 12 weeks before Randomization. Treatment-naïve subjects with AD can be entered into the study.

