9.5.1.3 Efficacy Assessments

9.5.1.3.1 PSYCHOMETRIC ASSESSMENTS

CDR: The CDR is a clinical global rating scale requiring the interviewing of both the subject and a study partner who knows and has contact with the subject. The CDR is a

clinician-directed assessment of both cognition and function, and is intended to capture the state and therefore the disease stage of the individual. The CDR has been proposed as an acceptable approach for following disease progression and confirming treatment in AD.

The CDR assesses 6 domains of subject function: memory, orientation, judgment, and problem solving, community affairs, home and hobbies and personal care. Each of these items has a maximum possible score of 3 points and the total score is a sum of the item scores (sum of boxes) giving a total possible score of 0 to 18 with higher scores indicating more impairment.

For any given subject, every effort should be made to ensure that the CDR rater remains unchanged throughout the study. (revised per Amendment 04)

ISLT: The ISLT is a verbal learning and episodic memory test assessing both immediate and delayed recall. Subjects are read a list of 12 items that can be obtained at the local shopping center. Subjects are asked to recall as many of the items as possible and this immediate recall trial is repeated 3 times. After a delay of approximately 20 to 30 minutes, in which time the CBB will be performed as a distractor task, subjects are again asked to recall as many of the words on the shopping list as they can (ie, a delayed recall trial).

MMSE: A 30-point scale that measures orientation to time and place, registration, immediate and delayed recall, attention, language, and drawing. Scores range from 0 (most impaired) to 30 (no impairment).

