9.7.1.6.1 PRIMARY EFFICACY ANALYSIS

The primary analysis will be based on an intent to treat philosophy without regard to adherence to treatment. The primary analysis of the change from baseline in CDR-SB at 24 months will be performed to compare elenbecestat 50 mg per day versus placebo using a linear mixed effects model for repeated measures (MMRM) on the FAS. The MMRM model will include fixed effects of treatment group, visit, treatment group by visit interaction, baseline CDR-SB, baseline CDR-SB by visit interaction, and randomization stratification variables (ie, region [7 levels], clinical dementia [yes, no], and concurrent AD medication use at randomization [Visit 2] [yes, no]). *ApoE4* status may be included in the model if appropriate. (revised per Amendments 01, 02, and 06) An unstructured covariance matrix will be employed to model the covariance of within subject effect; if MMRM fails to converge then a covariance structure with fewer parameters from the following list will be employed according to the prespecified order in the list until the MMRM converges. The list of covariance structure will include Heterogeneous Toeplitz, Toeplitz, Heterogeneous Compound Symmetry, and Compound Symmetry. This primary analysis will include all observed post baseline data of the change from baseline in CDR-SB without imputation of missing values. The treatment effect for elenbecestat versus placebo will be compared at 24 months based on MMRM model. The LS means and difference in LS means between elenbecestat treatment group and placebo, and corresponding 95% CI will be presented.

The null hypothesis is that there is no difference in the mean change from baseline in CDR-SB at 24 months between elenbecestat 50 mg per day and placebo. The corresponding alternative hypothesis is that there is a difference in the mean change from baseline in CDR-SB at 24 months between elenbecestat 50 mg per day and placebo.

The primary analysis will be repeated to minimize the impact of change in concomitant AD medications where efficacy data after initiation of new AD medications and increase of current AD medications will be censored.

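### The primary MMRM does not adjust for baseline ADAS-cog14, although it is scheduled before the first dose for every subject; adding it is a low-cost gain in precision, not the correction of an error.

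*Protocol*

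**What the plan says.** Section 9.7.1.6.1 (Primary Efficacy Analysis), and the synopsis in parallel, fix the covariates: "The MMRM model will include fixed effects of treatment group, visit, treatment group by visit interaction, baseline CDR-SB, baseline CDR-SB by visit interaction". The model also carries the stratification variables, namely "region [7 levels], clinical dementia [yes, no], and concurrent AD medication use at randomization [Visit 2] [yes, no". ApoE4 is left open: its "status may be included in the model if appropriate". The sensitivity ANCOVA after multiple imputation uses baseline CDR-SB, treatment and the stratification variables. Baseline ADAS-cog14 is in neither model.

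Section 9.1.2.1 (Treatment Period) places the scale among the Visit 2 assessments done "before the subject receives their first dose of study drug: MMSE, CDR, ADAS-cog14, FAQ, and NPI-10". Section 9.7.1.2 defines the Full Analysis Set (FAS) by a baseline and at least one post-dose value of the primary efficacy measure. It sets no requirement for ADAS-cog14.

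Section 9.7.2 sizes the trial with an unadjusted two-sample t test, so the sample size claims nothing from covariate adjustment.

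**The concern.** Baseline CDR-SB is the only continuous severity covariate in the primary model. Section 9.3.1 admits only subjects with a "CDR global score of 0.5" at Screening, on an instrument whose sum of boxes has a "total possible score of 0 to 18 with higher scores indicating more impairment". It is a reasonable inference that the baseline spread of CDR-SB is narrow and that this covariate can explain only a limited part of the Month 24 variance.

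A baseline performance-based cognitive score is already scheduled for everyone. If it predicts 24-month CDR-SB change beyond CDR-SB and dementia stage, leaving it out keeps residual variance in the primary comparison that could have been removed without collecting more data. Prespecified adjustment for a pre-dose covariate does not inflate type I error. What is at stake is the width of the confidence interval and a modest amount of power, not validity.

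**Working it through.** **Inputs** (Section 9.7.2 unless stated)

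- Placebo mean change 1.46; 25% reduction; difference = 0.25 × 1.46 = 0.365.
- Common SD 2.05; two-sided alpha 0.05; power 90%.
- 950 subjects per arm; 30% dropout; evaluable = 950 × 0.70 = 665 per arm.
- Incremental R², the share of residual Month 24 variance that baseline ADAS-cog14 explains beyond the covariates already in the model. The protocol gives no value, so 2%, 5% and 10% are assumptions.

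**Step 1: reproduce the stated sample size.**
n per arm = 2 × (1.960 + 1.282)² × 2.05² / 0.365² = 663 after rounding up. Dividing by 0.70 gives 948 per arm, 1896 in total. The exact t test needs 664 per arm, which gives 949 per arm and 1898 in total. The protocol states 1900. With 665 evaluable per arm the noncentral t power is 90.05%. The plan's figure reproduces.

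**Step 2: effect of one further covariate.**
Residual SD = 2.05 × √(1 − R²), and the standard error shrinks by the same factor √(1 − R²). An unadjusted trial of the same precision would need 1900 / (1 − R²) subjects. Power is by noncentral t at 665 per arm.

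| Assumed R² | Residual SD | SE ratio | Power | Equivalent N |
|---|---|---|---|---|
| 0 | 2.05 | 1.000 | 90.05% | 1900 |
| 0.02 | 2.03 | 0.990 | 90.6% | 1939 |
| 0.05 | 2.00 | 0.975 | 91.4% | 2000 |
| 0.10 | 1.94 | 0.949 | 92.8% | 2111 |

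**Step 3: change the reference point.**
Step 2 starts from the unadjusted t test, but the planned MMRM already adjusts for baseline CDR-SB and the strata. Suppose, again as an assumption, that these explain 10% of the variance. The starting SD is then 2.05 × √0.90 = 1.94 and the starting power is 92.8%. A further 2% or 10% of the remaining variance raises this to 93.3% or 95.0%. The gains are about 0.5 and 2.2 points, against about 0.6 and 2.7 points in Step 2.

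**Step 4: availability of the covariate.**
The schedule gives every randomized subject a pre-dose ADAS-cog14. Because the FAS requires a baseline of the primary measure only, a subject could belong to the FAS without one. A mixed model drops any record with a missing covariate, so an added term needs a rule for that case.

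**The case against.** The strongest reply is that nothing here is wrong. Baseline plus strata is a conventional MMRM, the trial meets its 90% target without covariate help, and the size of any gain cannot be derived from the protocol. That stands, and it limits the point to an efficiency suggestion.

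Several stronger readings are tempting, and the protocol does not support them.

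- *CDR-SB is the only severity measure in the model.* It is not. Clinical dementia (yes/no) is a direct stage factor in the same model, and concurrent AD medication is a partial proxy. CDR-SB is only the sole continuous one.
- *ADAS-cog14 is free of the truncation that affects CDR-SB.* This does not follow. Section 9.3.1 also requires MMSE of at least 24 and impaired ISLT recall, and ADAS-cog14 contains word-recall tasks, so its range is probably restricted indirectly. The CDR limit applies to the global score at Screening, the analysis baseline is taken at Visit 2, and no bound on CDR-SB is given.
- *Section 9.2.3 shows that ADAS-cog14 is the better covariate.* The description there, "considered more sensitive for less impaired populations such as MCI/Prodromal and mild AD subjects", justifies choosing the 14-item version as an outcome. It neither compares the scale with CDR-SB nor says that its baseline value predicts CDR-SB change.
- *Dropout handling is materially weakened.* CDR is measured every 3 months, and the MMRM uses all observed values. Earlier CDR-SB values are therefore likely to carry most of the information on a missing Month 24 value. Section 9.7.1.6.1 does not give the imputation model, which may be in the SAP.
- *ApoE4 should be made mandatory.* The revision history for Amendment 01 records the sponsor's view that it is not important for disease progression, and a final covariate choice of that kind is commonly left to the SAP.
- *The same terms are needed for ADCOMS.* That model already uses baseline ADCOMS, which contains four ADAS-cog items (Table 1), so the addition would be largely redundant.

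None of this makes the narrow change harmful or invalid.

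**Conclusion.** The point holds as a cheap improvement. Sections 9.7.1.6.1 and 9.1.2.1 together show a prespecified primary model that does not use a pre-dose cognitive score scheduled for all subjects. The planned analysis is valid and its sample size is correctly derived.

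The expected benefit is modest: roughly 0.6 to 2.7 power points for an assumed incremental R² of 2% to 10% against the unadjusted reference. It is less once the planned covariates are credited with explaining variance, and zero if baseline ADAS-cog14 adds nothing to CDR-SB and dementia stage. These figures assume 665 evaluable subjects per arm, a difference of 0.365 and an SD of 2.05. They treat the Month 24 comparison as an adjusted two-sample test, not as the full MMRM.

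**What to change.** In Section 9.7.1.6.1 and the matching synopsis text:

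1. Add baseline ADAS-cog14 and the baseline ADAS-cog14-by-visit interaction to the fixed effects of the primary MMRM.
2. Add baseline ADAS-cog14 as a covariate in the ANCOVA after multiple imputation.
3. State a treatment-blind rule for a missing baseline ADAS-cog14, for example single imputation of the covariate by its overall mean, so that no FAS subject is lost.

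The change should be made before unblinding and carried into the SAP. It costs a sentence or two and a few fixed-effect parameters, which are negligible at about 1900 subjects. No new data are collected and the sample size does not change.

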The null hypothesis is that there is no difference in the mean change from baseline in CDR-SB at 24 months between elenbecestat 50 mg per day and placebo. The corresponding alternative hypothesis is that there is a difference in the mean change from baseline in CDR-SB at 24 months between elenbecestat 50 mg per day and placebo.

The primary analysis will be repeated to minimize the impact of change in concomitant AD medications where efficacy data after initiation of new AD medications and increase of current AD medications will be censored.

The following sensitivity analysis will be conducted to evaluate the impact of missing data: the primary endpoint will be analyzed using analysis of covariance model (ANCOVA) after multiple

imputation. The ANCOVA model will include baseline CDR-SB as a covariate, with treatment group, and randomization stratification variables as factors. *ApoE4* status may be included in the model if appropriate. Additional sensitivity analyses will be performed to assess the robustness of the missing at randomization assumption in the primary MMRM model.

Subgroup analysis (eg, stratification factors and *ApoE4* status) and additional sensitivity analysis for the primary endpoint will be performed as appropriate. (revised per Amendments 01 and 06)

Analyses for Key Secondary Efficacy Endpoints (revised per Amendment 06)

The key secondary analyses will be performed only if the primary analysis is significant. The treatment effect for elenbecestat 50 mg/day versus placebo, for each key secondary efficacy endpoint, will be tested using a sequential testing procedure at a significance level of 2-sided alpha =0.05, ie, any test will start only if the test with higher hierarchical order is significant.

The change from baseline in ADCOMS at 24 months will be analyzed using the same MMRM model as the primary efficacy analysis to compare elenbecestat 50 mg per day versus placebo on the FAS, using baseline ADCOMS in the model.

The change from baseline in amyloid PET SUVR at 24 months will be analyzed using the same MMRM model as the primary efficacy analysis to compare elenbecestat 50 mg per day versus placebo on the FAS, using baseline amyloid PET SUVR in the model. The same analysis will be performed within study as key secondary efficacy endpoint analyses.

Analyses for Other Secondary Endpoints (revised per Amendment 06)

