Concomitant therapy with AChEI or memantine should only be allowed and/or acceptable for the region or country in which the study is being conducted and should follow the local standard of care for symptomatic treatment (revised per Amendment 02). Subjects who are taking AChEI or memantine will be required to be on a stable dose for at least 12 weeks before randomization. Initiation or termination of therapy or changing dose of AChEIs or memantine during the study should be undertaken in compliance with local standard of care for symptomatic treatment of AD. (revised per Amendments 03 and 06) Subjects who start on AChEI or memantine or change their dose during the Treatment Period will be permitted to continue in the study; however, subjects should not undertake cognitive assessments until they have been on a stable dose for at least 4 weeks.

Subjects who are taking other medications will be required to be on a stable dose for at least 4 weeks before randomization, except for medications which are administered as short courses (eg, up to 3 weeks unless discussed and agreed with the medical monitor) of treatment (eg, anti-infectives, oral steroids) or which are to be used on a PRN basis. (revised per Amendment 01) Concomitant medications (including opiates and short-term use of benzodiazepines) which are used on a PRN basis and which are central nervous system (CNS) active and may affect cognitive function are not permitted during a period of 72 hours before cognitive testing. (revised per Amendments 04 and 06)

For subjects who undergo an LP for collection of CSF: Subjects who are on anticoagulants may have a variable dose but should have stable anticoagulation control for at least 4 weeks before the LP procedure. Subjects may be required to stop their anticoagulant medication before CSF collection and then restart this medication after the LP procedure, as per local guidelines.

Either aspirin or clopidogrel (or any other antiplatelet drug that is not aspirin) is permitted in all subjects. Aspirin and clopidogrel (or any other antiplatelet drug which is not aspirin) in combination are also permitted but subjects who are on such a combination of antiplatelet drugs may be required to stop 1 or more of these antiplatelet drugs before the LP procedure and restart after the LP as per local guidelines.

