9.7.1.1.2 SECONDARY ENDPOINTS

The key secondary endpoints of the study are as follows (revised per Amendment 06):

- Change from baseline in ADCOMS at 24 months in the combined studies
- Change from baseline in amyloid PET SUVR at 24 months for brain amyloid levels in the combined studies
- Change from baseline in amyloid PET SUVR at 24 months for brain amyloid levels in the individual studies

The other secondary endpoints of the study are as follows (revised per Amendment 06):

- Change from baseline in the CDR-SB at 24 months for subjects enriched by baseline PET SUVR, eg, between 1.2 and 1.6, in the combined studies
- Change from baseline in the ADCOMS at 24 months for subjects enriched by baseline PET SUVR, eg, between 1.2 and 1.6, in the combined studies
- The rate of change over time (mean slope) based on CDR-SB score over 24 months in the combined studies
- Time to worsening of CDR scores by 24 months (eg, the worsening of global CDR score is defined as an increase from baseline by at least 0.5 points on the global CDR scale on 2 consecutive scheduled visits at which global CDR is undertaken) in the combined studies
- Time to conversion to dementia by 24 months for subjects who were not clinically staged as dementia at Baseline based on clinical diagnosis in the combined studies (revised per Amendment 01)
- Change from baseline in CDR-SB at 27 months (ie, 24 months of treatment plus 3 months posttreatment follow-up) in the combined studies (revised per Amendment 01)
- Change from baseline in ADAS-cog14, MMSE, and FAQ at 24 months in the combined studies
- Change from baseline in ADAS-cog14 Word List (immediate recall and delayed recall) at 24 months in the combined studies (revised per Amendment 01)

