Time to worsening of CDR scores by 24 months will be analyzed on the FAS using Cox regression model for treatment effect adjusting for randomization stratification factors. *ApoE4* status may be included in the model if appropriate. (revised per Amendment 06) Time to worsening of a CDR score is defined as time from randomization to worsening of the CDR score (ie, the first worsening in 2 consecutive scheduled visits). For subjects whose CDR scores have not worsened by the end of the Treatment Period of the Core Study, the time to worsening of the CDR score will be censored at the date of last CDR assessment for these subjects.

Time to conversion to dementia for subjects who were not clinically staged as dementia at Baseline based on clinical diagnosis will be analyzed on the FAS using Cox regression model for treatment effect adjusting for randomization stratification factors. *ApoE4* status may be included in the model if appropriate. (revised per Amendment 06) Proportion of subjects with

dementia diagnosis at 24 months will be estimated using Kaplan—Meier method based on time to conversion to dementia based on clinical diagnosis. Time to conversion to dementia for subjects who were not clinically staged as dementia at Baseline based on clinical diagnosis is defined as time from randomization to conversion to dementia based on clinical diagnosis. For subjects without clinical dementia by the end of study, the time to conversion to dementia based on clinical diagnosis will be censored at the date of last dementia diagnosis.

The other continuous secondary efficacy endpoints as defined above will be analyzed using the same MMRM model as the primary efficacy analysis to compare elenbecestat 50 mg per day versus placebo on the FAS, using baseline value corresponding to the response variable in the model.

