Immune globulin IV, IVIG, IGIV	Carimune, Flebogamma, Gamimune N, Gammagard, Gamunex, Gammar-P IV, Iveegam, Octagam, Panglobulin, Vigam, Polygam S/D, Privigen, Sandoglobulin, Venoglobulin-S
Denosumab	Prolia (revised per Amendment 02)
Other monoclonal antibodies not listed here	

^a Topical, ocular, and inhaled formulations with minimal systemic exposure need not be prohibited. (revised per Amendment 04)

Listing 3 Prohibited Live/Live Attenuated Vaccines Within 3 Months Before Randomization and Until the Last Visit During the Treatment Period (this does not apply to non-live/inactivated vaccines)

Bacterial vaccines	Viral vaccines
Bacillus Calmette-Guérin vaccine against tuberculosis	Measles vaccination
Typhoid vaccination (oral)	Mumps vaccination
Cholera vaccination (oral)	Rubella vaccination
	Oral polio vaccination (Sabin)
	Yellow fever vaccination
	Varicella (chickenpox) vaccination
	Rotavirus vaccination
	Japanese encephalitis vaccination
	Live attenuated influenza vaccine (FluMist in the United States and Canada, and Fluenz in Europe)

This list is not exhaustive

Permitted Prior/Concomitant Medications

Listing 4 Medications Which Need To Be on a Stable Dose for 12 Weeks Before the Cognitive Assessments at Visit 2

Cognitive Enhancers	
Donepezil	Aricept
Rivastigmine	Exelon
Galantamine	Reminyl
Memantine	Namenda

Initiation, termination or change in dose is permitted if in line with local standard of care. Any changes are required to be stable for 4 weeks before any cognitive assessments.

Herbal medications or preparations should be discussed with the medical monitor. However, if they have claims of cognitive enhancements then they should follow the same rules as the medications in this listing. (revised per Amendment 06)

**Listing 5 Medications Permitted if Used on PRN or Short Term Basis (2 to 4 Weeks)
Which Are Not to be Used Within 72 Hours Before Cognitive Testing**

Generic name	Trade name
Benzodiazepines (revised per Amendments 04 and 06)	
Estazolam	ProSom
Alprazolam	Alprazolam Intensol, Niravam, Xanax
Triazolam	Halcion
Midazolam	Versed
Lorazepam	Ativan
Flunitrazepam	Rohypnol
Temazepam	Restoril
Clonazepam	Ceberclon, Klonopin
Diazepam	Diastat, Dizac, Valium
Chlordiazepoxide	H-Tran, Librium
Flurazepam	Dalmane
Sedatives	
Zopiclone	(various)
Zolpidem	Ambien; others
Ramelteon	Rozerem
Amitriptyline	(various)
Dothiepin	(various)
Risperidone	Risperdal
Olanzapine	Zyprexa
Promethazine	Phenergan; others

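### The supportive CDR-SB repeat meant to limit the impact of AD-medication changes censors only after starts and increases, although stops and reductions are also permitted

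*Protocol*

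**What the plan says.** Section 9.7.1.6.1 makes the primary analysis an MMRM of CDR-SB change at 24 months, regardless of adherence. It then adds a supportive repeat. The synopsis gives the purpose in the same words: "The primary analysis will be repeated to minimize the impact of change in concomitant AD medications". The rule that follows in both places is that "efficacy data after initiation of new AD medications and increase of current AD medications will be censored".

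The changes allowed during the study are described more widely. Section 9.4.7 reads: "Initiation or termination of therapy or changing dose of AChEIs or memantine during the study should be undertaken in compliance with local standard of care". Listing 4 in Appendix 2 agrees: "Initiation, termination or change in dose is permitted if in line with local standard of care". Neither confines dose changes to increases. Both ask for a stable dose of 4 weeks before cognitive testing after a change.

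**The concern.** The repeat names change in AD medication as what it tries to neutralise, yet its rule acts on only two of the four kinds of change the protocol allows. A symptomatic drug that is started or increased would be expected, if anything, to improve scores. One that is stopped or reduced would be expected to worsen them. The rule removes data after the first kind and keeps data after the second.

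The resulting estimate answers neither natural question. It is not the effect regardless of background-medication changes, which the primary analysis already gives. Nor is it the effect had no such changes occurred. If stops or reductions differ by arm, for instance through tolerability, the repeat carries that difference while being read as an analysis that limits it. The 4-week stability requirement does not help, since it delays testing without removing the effect of the changed medication.

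**Working it through.** **Which changes does the rule reach?**

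| AChEI or memantine change | Permitted (9.4.7, Listing 4) | Censored in the repeat (9.7.1.6.1) |
|---|---|---|
| Initiation | Yes, named | Yes |
| Dose increase | Yes, as a change of dose | Yes |
| Dose reduction | Yes, as a change of dose | No |
| Termination | Yes, named | No |

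The protocol states no other rule for data after a stop or reduction.

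**Who is affected?** A subject who switches drugs is censored when the new one starts. A subject who starts or increases and later stops has already been censored. The gap is therefore confined to subjects on an AD drug at baseline who stop or reduce it with no earlier start or increase.

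**Benchmark.** Section 9.7.2 assumes a placebo change of 1.46, SD 2.05, a 25% reduction, 30% dropout, 90% power and two-sided alpha of 0.05.
- Planned difference: 0.25 × 1.46 = 0.365.
- Evaluable per arm, normal approximation: 2 × (1.960 + 1.282)² × 2.05² / 0.365² = 663.
- Randomized per arm: 663 / 0.70, rounded up to 948, or 1896 in total. The exact t calculation gives 1898.

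The stated 1900 is reproduced. No figure in the plan is in dispute.

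**Illustrative size.** The protocol gives neither a rate of stopping or reducing nor an effect of doing so, so both are assumed here. Let Δp be the between-arm difference in the share of all subjects in an arm who fall in the gap, and d the resulting worsening in CDR-SB. Relative to an estimate free of AD-medication changes,

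shift = Δp × d.

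| Δp (percentage points) | d = 0.25 | d = 0.5 | d = 1.0 |
|---|---|---|---|
| 2 | 0.005 (1.4%) | 0.010 (2.7%) | 0.020 (5.5%) |
| 5 | 0.0125 (3.4%) | 0.025 (6.8%) | 0.050 (13.7%) |
| 10 | 0.025 (6.8%) | 0.050 (13.7%) | 0.100 (27.4%) |

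Percentages are of 0.365. The right-hand column is generous: d = 1.0 is 1.0 / 1.46 = 68% of the assumed 24-month placebo decline. More stopping on placebo would inflate the apparent benefit; more stopping on elenbecestat would shrink it.

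**Cost of wider censoring.** Start from 950 × 0.70 = 665 evaluable per arm, where power is 90.1%. Losing a further 2%, 5% or 10% of Month 24 values leaves about 89.5%, 88.6% or 86.9%. This concerns the supportive repeat only.

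**The case against.** The best defence is consistency. Section 9.7.1.1.4 glosses change of concomitant AD treatment as a dose increase and/or initiation, and section 9.7.1.6.3 uses the same definition. The censoring rule names the same two events, so the choice looks deliberate. Section 9.4.7 tells sites what is allowed; it does not say what the analysis must censor. The aim is also only to minimise the impact. That shows the rule was not a slip, but it does not justify it here. The definition belongs to an exploratory endpoint on the need for more AD treatment, where counting only escalation makes sense. An analysis meant to limit background-medication effects has no such reason to be one-sided.

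Three further objections stand and limit the point. The affected group is narrow. Stops may follow progression or poor tolerability, so censoring them leans on missing at random and is not free of bias; keeping the scores would be conservative if stops were commoner on active drug. And nothing in the protocol suggests that stops differ by arm.

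A reader might also infer that the Month 27 CDR-SB endpoint ("Change from baseline in CDR-SB at 27 months (ie, 24 months of treatment plus 3 months posttreatment follow-up) in the combined studies") is undermined, because symptomatic drugs may be started after study drug ends and the repeat covers only Month 24. The document does not support that. Month 27 is an other secondary endpoint outside the testing hierarchy. Its role in separating elenbecestat from symptomatic drugs appears only in the revision-history rationale for Version 2.0, which says it will aid that distinction. Starts must follow local standard of care. A medication-censored repeat for Month 27 or ADCOMS is detail that a statistical analysis plan, not shown here, could supply.

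**Conclusion.** The point holds as a minor one. The supportive Month 24 repeat states an aim covering change in AD medication and fixes a rule that handles such change in one direction only, while the protocol permits it in both. The possible distortion of that repeat is about 0.005 to 0.10 CDR-SB points, or 1% to 27% of the planned 0.365, in either direction. This rests entirely on the assumed ranges for Δp and d.

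It would be wrong to infer that the primary result is biased. The primary MMRM is treatment-regardless by design, and neither the sample size nor any test in the hierarchy depends on this repeat. Nor can it be said that the rule favours elenbecestat, since the direction depends on which arm stops or reduces more.

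**What to change.** In section 9.7.1.6.1 and the matching synopsis paragraph, reword the supportive repeat so that efficacy data are censored after any post-randomization change in AChEI or memantine: initiation, increase, reduction or termination. Keep the treatment-regardless MMRM as primary. This changes an analysis rule only and takes no position on which medication changes sites should allow.

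The cost is a phrase of text, slightly fewer data points in a supportive analysis, and reliance on missing at random after stops and reductions. No new data are needed, because Table 5 records concomitant medications at every visit.

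Optional: a matching repeat for Month 27 CDR-SB, with a by-arm table of AD-medication changes after Month 24. Table 5 already collects medications and CDR at Visits 14 and 15.
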